22.1.2 POOLABILITY OF CENTERS

Using the LME modeling approach outlined above, poolability will be evaluated across centers by including fixed effects for Center and Treatment by Center interaction in the model and applying a likelihood ratio test. If the TxC interaction is significant at $\alpha=0.15$ a Center effect will be included in the final model and the results will be reported separately by Center. For this analysis, Centers with less than 5 enrolled subjects will be combined into a single virtual center.

22.1.3 MISSING DATA

Note that since the primary analysis uses maximum likelihood methods on the complete data then any MAR (missing at random) imputation model should provide essentially equivalent results. That is, the missing data are ignorable if they are MAR and we are using full maximum likelihood estimation. However, as a sensitivity analysis, missing data for the primary TBUT outcome at the 1 month time point will be imputed using baseline characteristics and 2-week outcomes. In this, we follow the advice in sections 2.8 and 2.10 of “Multiple Imputation and its Application”⁵² to use an imputation model that is more complex than the final analysis model. In order to carry out the imputations we will fit a linear model that predicts TBUT change at 1 month using TBUT at baseline and 2 weeks, along with other covariates, as predictors. Based on pilot study data, we expect that 1 month outcomes will be strongly predicted by intermediate (2 week) results. Using predicted 4-week means and variances from this model we can create multiple imputations for the missing 4-week TBUT changes. Results from the multiple imputations will be combined using Rubin’s method.

Further sensitivity analysis can be carried out by extending the mixed effects model for the primary analysis described above to also include repeated measurements across time for each patient and eye. Under this model we can carry out maximum likelihood estimation that allows for one of the two (Week 2, Week 4) measurements for each person to be missing.

22.1.4 SECONDARY EFFECTIVENESS ENDPOINTS

If the primary endpoint is successful (if the null hypothesis for the primary endpoint is rejected) then the secondary endpoints will be tested using a hierarchical testing procedure as described in 12.5.5 based on the Cohort 2 subjects.

The secondary effectiveness outcomes of the Cohort 1 subjects will be summarized separately by descriptive statistics (mean, median, standard deviation, minimum, and maximum for continuous variables; count and percent for categorical variables).

22.2 SAFETY ENDPOINTS AND ANALYSIS

22.2.1 DESCRIPTIVE ANALYSES

All adverse events, measures of pain and discomfort, changes in ocular surface staining, changes in IOP, and changes in BCVA (EDTRS) will be tabulated by visit and treatment group.

⁵² Carpenter, J., and Kenward, M. *Multiple Imputation and its Application* (2013), Wiley UK.

22.2.2 PRIMARY SAFETY ENDPOINT

The primary safety endpoint is the incidence of ocular adverse events.

22.2.3 PRIMARY SAFETY ANALYSIS

The primary safety endpoint will be summarized for each treatment group, for each Cohort and overall.

We will compute the incidence of ocular adverse events as a simple proportion, counting the number of subjects with any event (that is, counting the first event per person).

For the simple proportion, we will calculate the 95% CIs using the Agresti and Coull “ADD2” method⁵³.

22.2.4 SECONDARY SAFETY ENDPOINTS

The secondary safety endpoints include:

- Discomfort/pain during treatment
- Change in best corrected visual acuity (ETDRS)
- Change in intraocular pressure (IOP)

These endpoints will be summarized by treatment group and visit, for each Cohort and overall.

22.3 SAMPLE SIZE CALCULATIONS

Sample size calculations were originally carried out prior to the modification of the SmartLid device. After device modification the trial was “restarted”, with Cohort 2 retaining the original sample size of 138 subjects. The subjects initially enrolled in Cohort 1 (up to 100 subjects) will be used in supplemental analyses and to provide additional safety information.

Since the study success criteria is that TearCare will be non-inferior to the control for both TBUT and MEIB, we will calculate the required sample size for Tear Break-Up Time (TBUT) and total Meibomian gland secretion score (MEIB) separately. A power of 95% for each of these two outcomes will produce an overall experiment-wise power between 90.25% (if TBUT and MEIB are uncorrelated), and 95% (if TBUT and MEIB are perfectly correlated).

⁵³ Agresti, A., and B.A. Coull (1998) Approximate is better than “exact” for interval estimation of binomial proportions. *American Statistician* 52:119-126.

The primary Tear Breakup Time (TBUT) and total Meibomian gland secretion score (MEIB) endpoints are measured on a per-eye basis. In order to account for the correlation between eyes the sample size is calculated in two steps. The first step is to carry out a standard sample size calculation for the number of eyes based on a two-sample t-test with unequal variances. This test is appropriate for a sample of independent eyes from the two groups, that is, a study in which only one eye per subject is enrolled. The second step is to allow for two eyes per subject by adjusting the independent sample size to account for the correlation between eyes.⁵⁴ This is done by multiplying by a “design effect” (DEFF) that can be calculated from the pilot study data (described in Section 5.2.2). Finally we allow for some loss to follow up and then divide by 2 (eyes per subject) to arrive at a final enrolled sample size in terms of number of subjects.

This sample size calculation does not account for the adjustment for baseline in the analysis models. That adjustment should only serve to increase the power of the test, so the simpler calculation is conservative in that sense.

22.3.1 TEAR BREAKUP TIME

For the TBUT sample size calculation, we assume the same positive treatment effect for TearCare and for LipiFlow, reducing the TBUT time per eye by 3 seconds, with a standard deviation of 6.0 seconds. The standard deviation for the change from baseline to 1 month was (conservatively) estimated for TearCare from the pilot data, and for LipiFlow from published results⁵⁵.

The sample size is calculated under the following assumptions:

- a one-sided $\alpha = 0.05$ t-test for non-inferiority,
- with a NI margin of 3.0 seconds,
- to obtain 95% power.

The non-inferiority margin was based on published LipiFlow variability⁵⁵. Under these assumptions the required sample size is 176 eyes, 88 eyes per treatment group.

The design effect for a clustered sample when randomization is at the cluster level is calculated as $DEFF = 1 + \delta(m - 1)$ where δ is the intraclass correlation and m is the

⁵⁴ Campbell M, Walters, S. How to Design, Analyse and Report Cluster Randomised Trials in Medicine and Health Related Research. Wiley UK, 2014.

⁵⁵ Lane, S.S, H.B. DuBiner, R.J. Epstein, P.H. Earnest, J.V. Greiner, D.R. Hardten, E.J. Holland, M.A. Lemp, J.E. McDonald II, D.I. Silbert, C.A. Blackie, C.A. Stevens, and R. Bedi. A New System, the LipiFlow, for the Treatment of Meibomian Gland Dysfunction. Cornea 2012; 31(4): 396-404.

average size of the clusters in the sample⁵⁶. Here $m=2$ so $DEFF = 1 + \delta$. To estimate the intraclass correlation we fit a linear mixed effects model with a random intercept for subjects to obtain estimates of σ_a^2 and σ_e^2 . Using these we can estimate the intraclass correlation as $\delta = \sigma_a^2 / (\sigma_a^2 + \sigma_e^2)$. From the TearCare pilot data the estimates of the variance components for TBUT are $\hat{\sigma}_a^2 = 1.92$ and $\hat{\sigma}_e^2 = 3.39$, giving a DEFF of 1.36. We will assume that the intraclass correlation for LipiFlow is the same as TearCare. So the sample size calculated using the t-test formulas will be inflated by 1.4 to account for correlation between eyes. Thus the DEFF-adjusted sample size is 246 eyes.

Finally, we will assume that 10% of the enrolled subjects (eyes) will be lost to follow-up. The resulting sample size is 274 enrolled eyes, or 137 enrolled subjects (which we round up to 69 per group).

22.3.2 MEIBOMIAN GLAND SECRETION SCORE

For the MEIB sample size calculation, we assume the same positive treatment effect for TearCare and for LipiFlow, reducing the total Meibomian gland secretion score per eye by 9 units, with a standard deviation of 9.0. The standard deviation for the change from baseline to 1 month was (conservatively) estimated for TearCare from the pilot data, and for LipiFlow from published results⁵⁵.

The sample size is calculated under the following assumptions:

- a one-sided $\alpha= 0.05$ t-test for non-inferiority,
- with a NI margin of 5.0 units,
- to obtain 95% power.

The non-inferiority margin was based on published LipiFlow variability⁵⁵. Under these assumptions the required sample size is 142 eyes, 71 eyes per treatment group.

From the TearCare pilot data the estimates of the variance components for MEIB are $\hat{\sigma}_a^2 = 15.93$ and $\hat{\sigma}_e^2 = 20.11$, giving a DEFF of 1.44. We will assume that the intraclass correlation for LipiFlow is the same as TearCare. So the sample size calculated using the t-test formulas will be inflated by 1.5 to account for correlation between eyes. Thus the DEFF-adjusted sample size is 213 eyes.

Finally, we will assume that 10% of the enrolled subjects (eyes) will be lost to follow-up. The resulting sample size is 237 enrolled eyes, or 119 enrolled subjects (which we round up to 60 per group).

⁵⁶ Campbell M, Walters, S. How to Design, Analyse and Report Cluster Randomised Trials in Medicine and Health Related Research. Wiley UK, 2014.

22.3.3 SAFETY

For a safety sample of size 238 TearCare eyes (from Cohort 1 and Cohort 2) (since the expected AE rates are quite low there is unlikely to be any meaningful correlation between eyes), if the true incidence rate of ocular adverse events is 2.0% or less then the upper 95% one-sided confidence limit for the AE rate will be less than 6% with probability approximately 0.95. In other words, the power to reject a null of 6% if the true rate is 2.0% is 95%.

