12.6.3 PRIMARY SAFETY ANALYSIS

All adverse events will be reported by treatment group and AE category. Any serious adverse events will be completely described in the study report. The primary safety endpoint will be summarized for each treatment group.

We will compute the incidence of ocular events in two ways: first as a simple proportion, counting the number of subjects with any event (that is, counting the first event per person in either eye), then as an incidence rate, counting all events including repeated events per subject.

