12.7 SAMPLE SIZE CALCULATION

Up to 100 Cohort 1 subjects and 138 Cohort 2 subjects, approximately 119 in the TearCare group and 119 in the LipiFlow group, will be enrolled and randomized in the study. Sample size was calculated to provide more than 90% power to meet both the TBUT and MEIB effectiveness endpoints in Cohort 2 and sufficient precision around the

adverse event estimates. The sample size also takes into account an estimated 10% dropout rate. Details of the sample size calculation can be found in Appendix B.

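### The 95% safety power in SAP 22.3.3 is right for 238 independent eyes and a one-sided limit, but the planned analysis is a per-subject proportion with an ADD2 interval, for which no reading gives 95%

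*Combined protocol and SAP*

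**What the plan says.** Section 22.3.3 sets the safety precision. It begins "For a safety sample of size 238 TearCare eyes (from Cohort 1 and Cohort 2", treats the two eyes of a subject as effectively uncorrelated because events are expected to be rare, and states that at a true ocular event rate of 2.0% or less, "the upper 95% one-sided confidence limit for the AE rate will be less than 6% with probability approximately 0.95". It then rephrases this as power: "the power to reject a null of 6% if the true rate is 2.0% is 95" percent. It names no interval method and does not say whether 2% and 6% are per eye or per subject.

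The planned analysis counts subjects. Protocol 12.6.3 describes "counting the number of subjects with any event (that is, counting the first event per person in either eye", and SAP 22.2.3 has the same measure: "counting the number of subjects with any event (that is, counting the first event per person". For the interval, 22.2.3 says "For the simple proportion, we will calculate the 95% CIs using the Agresti and Coull" ADD2 method, without giving its sidedness. Protocol 12.6.3 also plans an event rate that counts repeat events, with no interval or power. Neither section plans a proportion of eyes.

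On numbers, 12.7 expects "approximately 119 in the TearCare group and 119 in the LipiFlow group" over both cohorts. Section 22.3 says that Cohort 1 subjects "will be used in supplemental analyses and to provide additional safety information". Section 22.3.4, however, attaches adequate precision for adverse event estimates to the 138 Cohort 2 subjects, 69 per group.

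**The concern.** The planning figure and the planned estimate differ in unit (eyes against subjects), in interval (a one-sided limit against a 95% ADD2 interval of unstated sidedness) and, in 22.3.4, in cohort. A reader of 22.3.3 would expect the trial to be able to exclude a 6% ocular event rate with 95% probability. The reported proportion will be of subjects, so that expectation needs checking on the subject scale with the named method.

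What is at stake is the stated precision of the primary safety endpoint. In the readable text, 22.3.3 is the only figure behind the general precision claims in 12.7 and 22.3.4; one figure in 22.3.4 could not be read.

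**Working it through.** **Inputs.** True rate 2%, threshold 6%, 238 TearCare eyes, one-sided 95% limit (22.3.3). About 119 TearCare subjects (12.7; 238/2 = 119). Cohort 2: 69 TearCare subjects, so 138 TearCare eyes (22.3.4). ADD2 interval (22.2.3). No dropout is applied, because 12.1 makes every subject with an attempted treatment evaluable for safety.

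**Method.** Find the largest event count c whose upper limit is below the threshold; power is P(X ≤ c) under the binomial at the true rate.
- Exact limit U: solves P(X ≤ x | n, U) = α.
- ADD2: p̃ = (x+2)/(n+4) and U = p̃ + z·√[p̃(1−p̃)/(n+4)], with z = 1.645 one-sided or 1.96 two-sided.

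**Step 1: the plan's figure.** n = 238, exact one-sided: x = 8 gives U = 5.98% and x = 9 gives 6.51%, so c = 8 and P(X ≤ 8 | 238, 0.02) = 0.948. The stated 95% reproduces.

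**Step 2: convert to subjects.** If the rates are per eye and eyes are independent, as 22.3.3 assumes, a subject has an event in either eye with probability 1 − 0.98² = 3.96% (true) and 1 − 0.94² = 11.64% (threshold).

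**Step 3: apply ADD2.** Example with n = 119, two-sided, x = 6: p̃ = 8/123 = 0.0650; U = 0.0650 + 1.96·√(0.0650 × 0.9350/123) = 0.1086, below 0.1164. At x = 7, U = 0.1192. So c = 6 and P(X ≤ 6 | 119, 0.0396) = 0.807.

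| Basis | True v threshold | ADD2 one-sided | ADD2 two-sided |
|---|---|---|---|
| 238 eyes | 2% v 6% | c = 7, 0.893 | c = 6, 0.798 |
| 119 subjects, rates per eye | 3.96% v 11.64% | c = 7, 0.899 | c = 6, 0.807 |
| 119 subjects, rates per subject | 2% v 6% | c = 2, 0.574 | c = 1, 0.310 |

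**Step 4: what causes the loss.** With ADD2 held fixed, rows 1 and 2 are level, so on the per-eye reading the change of unit costs no power. The gap from 0.948 comes from the interval method and, if two-sided, from the level. With an exact one-sided limit instead, moving from eyes to subjects does take 0.948 to 0.899, but that is discreteness: the attained type I error falls from 0.049 to 0.027. The unit itself cuts power only in row 3.

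**Step 5: Cohort 2 alone.** 138 TearCare eyes, exact one-sided, 2% v 6%: x = 3 gives 5.52% and x = 4 gives 6.51%, so c = 3 and power is 0.701. With two-sided ADD2, c = 2 and power is 0.477.

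**Step 6: limits for a restated sentence.** Take the smallest x with P(X ≤ x) ≥ 0.95 and report its two-sided ADD2 upper limit.

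| n | True subject rate | x | P(X ≤ x) | Upper limit |
|---|---|---|---|---|
| 119 | 3.96% | 8 | 0.953 | 13.0% |
| 69 | 3.96% | 6 | 0.981 | 18.1% |
| 119 | 2% | 5 | 0.967 | 9.8% |
| 69 | 2% | 3 | 0.950 | 12.6% |

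**The case against.** The best defence is that 22.3.3 states its own terms (eyes, one-sided, both cohorts) and is arithmetically right on them, while 22.2.3 only summarises the endpoint with an interval. A planning statement and a descriptive interval can coexist, and no test or success rule depends on 6%. This stands, and it is why the point is minor. It does not make the stated 95% describe the estimate that will be reported.

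A reader might infer that counting subjects drops power from 95% to 81%. The documents do not support that: ADD2 on 238 eyes already gives 80% two-sided, and the two-sided level is itself an assumption.

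A reader might also take 31% as the trial's real safety power. That needs per-subject rates, whereas the sample in eyes and the remark on between-eye correlation point to per-eye rates. It is also depressed by discreteness: the cutoff of one event has an attained error of 0.0055 against a nominal 0.025, and an exact two-sided limit gives 0.574 for the same rates.

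On cohorts, 12.7 names both and 22.2.3 reports each cohort and overall, so the conflict is confined to how 22.3.4 is worded.

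**Conclusion.** The point holds as a minor correction to a planning figure. The 95% belongs to 238 independent eyes with a one-sided exact limit. For the planned per-subject ADD2 analysis, power is about 90% one-sided or 81% two-sided on the per-eye reading, and 57% or 31% on the per-subject reading. No combination of unit and sidedness under ADD2 reaches 95%.

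The substantive effect of counting subjects is on the rate excluded: under independence, 6% per eye is 11.6% per subject. Separately, Cohort 2 alone gives 0.70 on the basis of 22.3.3, so the claim in 22.3.4 is not supported by the preceding section.

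These results assume about 119 TearCare subjects and, on the per-eye reading, independent eyes, which is the SAP's own assumption. Correlation would matter: an assumed between-eye correlation of 0.5 gives subject rates of 2.98% v 8.82% and two-sided ADD2 power of 0.718. Power does not fall smoothly with correlation, because the event cutoff moves in whole numbers.

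A reader might infer that a safety conclusion of the trial is at risk. It is not, since no safety decision rule uses 6%.

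**What to change.** In 22.3.3, label 2% and 6% as per eye or per subject, state the sidedness of the ADD2 interval, and restate the figure for about 119 TearCare subjects.
- **Rates per eye**, with independence kept as an explicit assumption: about 90% (one-sided) or 81% (two-sided) power to exclude 11.6% per subject. If two-sided, the alternative is an upper limit at or below 13.0% with at least 95% probability.
- **Rates per subject**, with no independence assumption needed: 57% or 31% power to exclude 6%, or a two-sided upper limit at or below 9.8% with at least 95% probability.

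In 22.3.4 and 12.7, say that the safety precision rests on both cohorts combined. Otherwise give the Cohort 2 figure for 69 TearCare subjects: a two-sided ADD2 upper limit of 18.1% on per-eye rates or 12.6% on per-subject rates. Both sections should refer to the restated 22.3.3.

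The cost is wording in three sections and a less favourable stated figure. No extra subjects, data or analyses are needed.

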22.3.4 SAMPLE SIZE SUMMARY

[figure not shown]
Based on the calculations outlined above, an overall enrolled sample of 138 individuals in Cohort 2, with 69 in each treatment group (total of 276 enrolled eyes) will provide more than 90% power for the combined TBUT and MEIB effectiveness endpoints and sufficient precision around the adverse event estimates. The initial 90-100 subjects enrolled in Cohort 1 will be used for supplemental analyses.

23 APPENDIX C – PREPARING FLUORESCEIN AND LISSAMINE GREEN SOLUTIONS

Use the method described by Gyau et al to prepare the fluorescein and lissamine green solutions.⁵⁷

23.1 PREPARING FLUORESCEIN SOLUTION

1. Put on a pair of sterile gloves.
2. Cut three (3) 1.0 mg Fluorescein Sodium Ophthalmic strips at the end of the colored portion of the strip using sterile scissors and tear each portion into 3 pieces. You should have 9 pieces.

[figure not shown]

3. Place the 9 pieces into a disposable microcentrifuge tube.

23.2 PREPARING LISSAMINE GREEN SOLUTION

1. Put on a pair of sterile gloves.
2. Cut three (3) Lissamine Green strips at the end of the colored portion of the strip using sterile scissors and tear each portion into 3 pieces. You should have 9 pieces.

⁵⁷ Gyau DA, Begley CF, Nelson JD. A simple cost effective method for preparing FL and LG solutions. Ocular Surface. 2018;16:139-145.

3. Place the 9 pieces into a disposable microcentrifuge tube.

24 APPENDIX D - DECLARATION OF HELSINKI

I. PREAMBLE

1. The World Medical Association (WMA) has developed the Declaration of Helsinki as a statement of ethical principles for medical research involving human subjects, including research on identifiable human material and data.

The Declaration is intended to be read as a whole and each of its constituent paragraphs should be applied with consideration of all other relevant paragraphs.

2. Consistent with the mandate of the WMA, the Declaration is addressed primarily to physicians. The WMA encourages others who are involved in medical research involving human subjects to adopt these principles.

II. GENERAL PRINCIPLES

1. The Declaration of Geneva of the WMA binds the physician with the words, "The health of my patient will be my first consideration," and the International Code of Medical Ethics declares that, "A physician shall act in the patient's best interest when providing medical care."
2. It is the duty of the physician to promote and safeguard the health, well-being and rights of patients, including those who are involved in medical research. The physician's knowledge and conscience are dedicated to the fulfilment of this duty.

3. Medical progress is based on research that ultimately must include studies involving human subjects.
4. The primary purpose of medical research involving human subjects is to understand the causes, development and effects of diseases and improve preventive, diagnostic and therapeutic interventions (methods, procedures and treatments). Even the best proven interventions must be evaluated continually through research for their safety, effectiveness, efficiency, accessibility and quality.
5. Medical research is subject to ethical standards that promote and ensure respect for all human subjects and protect their health and rights.
6. While the primary purpose of medical research is to generate new knowledge, this goal can never take precedence over the rights and interests of individual research subjects.
7. It is the duty of physicians who are involved in medical research to protect the life, health, dignity, integrity, right to self-determination, privacy, and confidentiality of personal information of research subjects. The responsibility for the protection of research subjects must always rest with the physician or other health care professionals and never with the research subjects, even though they have given consent.
8. Physicians must consider the ethical, legal and regulatory norms and standards for research involving human subjects in their own countries as well as applicable international norms and standards. No national or international ethical, legal or regulatory requirement should reduce or eliminate any of the protections for research subjects set forth in this Declaration.
9. Medical research should be conducted in a manner that minimizes possible harm to the environment.
10. Medical research involving human subjects must be conducted only by individuals with the appropriate ethics and scientific education, training and qualifications. Research on patients or healthy volunteers requires the supervision of a competent and appropriately qualified physician or other health care professional.
11. Groups that are underrepresented in medical research should be provided appropriate access to participation in research.

12. Physicians who combine medical research with medical care should involve their patients in research only to the extent that this is justified by its potential preventive, diagnostic or therapeutic value and if the physician has good reason to believe that participation in the research study will not adversely affect the health of the patients who serve as research subjects.
13. Appropriate compensation and treatment for subjects who are harmed as a result of participating in research must be ensured.

III. RISKS, BURDENS AND BENEFITS

- In medical practice and in medical research, most interventions involve risks and burdens.

Medical research involving human subjects may only be conducted if the importance of the objective outweighs the risks and burdens to the research subjects.

- All medical research involving human subjects must be preceded by careful assessment of predictable risks and burdens to the individuals and groups involved in the research in comparison with foreseeable benefits to them and to other individuals or groups affected by the condition under investigation.

Measures to minimize the risks must be implemented. The risks must be continuously monitored, assessed and documented by the researcher.

- Physicians may not be involved in a research study involving human subjects unless they are confident that the risks have been adequately assessed and can be satisfactorily managed.

When the risks are found to outweigh the potential benefits or when there is conclusive proof of definitive outcomes, physicians must assess whether to continue, modify or immediately stop the study.

IV. VULNERABLE GROUPS AND INDIVIDUALS

- Some groups and individuals are particularly vulnerable and may have an increased likelihood of being wronged or of incurring additional harm.

All vulnerable groups and individuals should receive specifically considered protection.

- Medical research with a vulnerable group is only justified if the research is responsive to the health needs or priorities of this group and the research cannot be carried out in a non-vulnerable group. In addition, this group should stand to benefit from the knowledge, practices or interventions that result from the research.

V. SCIENTIFIC REQUIREMENTS AND RESEARCH PROTOCOLS

- Medical research involving human subjects must conform to generally accepted scientific principles, be based on a thorough knowledge of the scientific literature, other relevant sources of information, and adequate laboratory and, as appropriate, animal experimentation. The welfare of animals used for research must be respected.
- The design and performance of each research study involving human subjects must be clearly described and justified in a research protocol.

The protocol should contain a statement of the ethical considerations involved and should indicate how the principles in this Declaration have been addressed. The protocol should include information regarding funding, sponsors, institutional affiliations, potential conflicts of interest, incentives for subjects and information regarding provisions for treating and/or compensating subjects who are harmed as a consequence of participation in the research study.

In clinical trials, the protocol must also describe appropriate arrangements for post-trial provisions.

VI. RESEARCH ETHICS COMMITTEES

- The research protocol must be submitted for consideration, comment, guidance and approval to the concerned research ethics committee before the study begins. This committee must be transparent in its functioning, must be independent of the researcher, the sponsor and any other undue influence and must be duly qualified. It must take into consideration the laws and regulations of the country or countries in which the research is to be performed as well as applicable international norms and standards but these must not be allowed to reduce or eliminate any of the protections for research subjects set forth in this Declaration.

The committee must have the right to monitor ongoing studies. The researcher must provide monitoring information to the committee, especially information about any serious adverse events. No amendment to the protocol may be

made without consideration and approval by the committee. After the end of the study, the researchers must submit a final report to the committee containing a summary of the study's findings and conclusions.

VII. PRIVACY AND CONFIDENTIALITY

- Every precaution must be taken to protect the privacy of research subjects and the confidentiality of their personal information.

VIII. INFORMED CONSENT

- Participation by individuals capable of giving informed consent as subjects in medical research must be voluntary. Although it may be appropriate to consult family members or community leaders, no individual capable of giving informed consent may be enrolled in a research study unless he or she freely agrees.
- In medical research involving human subjects capable of giving informed consent, each potential subject must be adequately informed of the aims, methods, sources of funding, any possible conflicts of interest, institutional affiliations of the researcher, the anticipated benefits and potential risks of the study and the discomfort it may entail, post-study provisions and any other relevant aspects of the study. The potential subject must be informed of the right to refuse to participate in the study or to withdraw consent to participate at any time without reprisal. Special attention should be given to the specific information needs of individual potential subjects as well as to the methods used to deliver the information.

After ensuring that the potential subject has understood the information, the physician or another appropriately qualified individual must then seek the potential subject's freely-given informed consent, preferably in writing. If the consent cannot be expressed in writing, the non-written consent must be formally documented and witnessed.

All medical research subjects should be given the option of being informed about the general outcome and results of the study.

- When seeking informed consent for participation in a research study the physician must be particularly cautious if the potential subject is in a dependent relationship with the physician or may consent under duress. In such situations the informed consent must be sought by an appropriately qualified individual who is completely independent of this relationship.

- For a potential research subject who is incapable of giving informed consent, the physician must seek informed consent from the legally authorized representative. These individuals must not be included in a research study that has no likelihood of benefit for them unless it is intended to promote the health of the group represented by the potential subject, the research cannot instead be performed with persons capable of providing informed consent, and the research entails only minimal risk and minimal burden.
- When a potential research subject who is deemed incapable of giving informed consent is able to give assent to decisions about participation in research, the physician must seek that assent in addition to the consent of the legally authorized representative. The potential subject's dissent should be respected.
- Research involving subjects who are physically or mentally incapable of giving consent, for example, unconscious patients, may be done only if the physical or mental condition that prevents giving informed consent is a necessary characteristic of the research group. In such circumstances the physician must seek informed consent from the legally authorized representative. If no such representative is available and if the research cannot be delayed, the study may proceed without informed consent provided that the specific reasons for involving subjects with a condition that renders them unable to give informed consent have been stated in the research protocol and the study has been approved by a research ethics committee. Consent to remain in the research must be obtained as soon as possible from the subject or a legally authorized representative.
- The physician must fully inform the patient which aspects of their care are related to the research. The refusal of a patient to participate in a study or the patient's decision to withdraw from the study must never adversely affect the patient-physician relationship.
- For medical research using identifiable human material or data, such as research on material or data contained in biobanks or similar repositories, physicians must seek informed consent for its collection, storage and/or reuse. There may be exceptional situations where consent would be impossible or impracticable to obtain for such research. In such situations the research may be done only after consideration and approval of a research ethics committee.

IX. USE OF PLACEBO

- The benefits, risks, burdens and effectiveness of a new intervention must be tested against those of the best proven intervention(s), except in the following circumstances:

Where no proven intervention exists, the use of placebo, or no intervention, is acceptable; or

Where for compelling and scientifically sound methodological reasons the use of any intervention less effective than the best proven one, the use of placebo, or no intervention is necessary to determine the efficacy or safety of an intervention

and the patients who receive any intervention less effective than the best proven one, placebo, or no intervention will not be subject to additional risks of serious or irreversible harm as a result of not receiving the best proven intervention.

Extreme care must be taken to avoid abuse of this option.

X. POST-TRIAL PROVISIONS

- In advance of a clinical trial, sponsors, researchers and host country governments should make provisions for post-trial access for all participants who still need an intervention identified as beneficial in the trial. This information must also be disclosed to participants during the informed consent process.

XI. RESEARCH REGISTRATION AND PUBLICATION AND DISSEMINATION OF RESULTS

- Every research study involving human subjects must be registered in a publicly accessible database before recruitment of the first subject.
- Researchers, authors, sponsors, editors and publishers all have ethical obligations with regard to the publication and dissemination of the results of research. Researchers have a duty to make publicly available the results of their research on human subjects and are accountable for the completeness and accuracy of their reports. All parties should adhere to accepted guidelines for ethical reporting. Negative and inconclusive as well as positive results must be published or otherwise made publicly available. Sources of funding, institutional affiliations and conflicts of interest must be declared in the publication. Reports of research not in accordance with the principles of this Declaration should not be accepted for publication.

XII. UNPROVEN INTERVENTIONS IN CLINICAL PRACTICE

In the treatment of an individual patient, where proven interventions do not exist or other known interventions have been ineffective, the physician, after seeking expert advice, with informed consent from the patient or a legally authorized representative, may use an unproven intervention if in the physician's judgment it offers hope of saving life, re-establishing health or alleviating suffering. This intervention should subsequently be made the object of research, designed to evaluate its safety and efficacy. In all cases, new information must be recorded and, where appropriate, made publicly available.
